## 8.1.2 Accrual Estimates

It is estimated that 1-2 subject will be enrolled per month, and approximately 36 months will be required to complete accrual and data acquisition to the study. In the case of subjects being unevaluable for analysis of primary endpoint, additional subjects may be enrolled to reach the required total number of evaluable subjects.

### 8.2 Imaging Analysis

For the analysis and interpretation of the HP C MR imaging data, we will utilize the opensource DICOM software package (SIVIC) to align, display and quantitatively interrogate multiparametric imaging data. Tumor regions of interest (ROIs) will be drawn to quantify MR biomarker (peak lactate/pyruvate ratio, lactate /pyruvate AUC, kPL) values across the selected volumes of interest. The peak lactate/pyruvate ratio, lactate /pyruvate AUC, kPL represent different methods of analyzing the pyruvate to lactate metabolic conversion.

#### 8.3 Analysis Plans

Data from all subjects dosed in the study will be included in all listings, plots, summary tables, and statistical analyses when appropriate. Missing values will not be substituted by estimated values, but treated as missing in the statistical evaluation.

In this pilot study, we will focus on the primary PDA HP C pyruvate metabolism (if present) because accurate assessment of treatment response in the primary PDA is particularly challenging on conventional imaging given its infiltrative nature(10). If the primary tumor has been resected, we will then focus our analysis on the largest abdominal metastasis that is amenable to HP MRI.

We will not explicitly adjust for multiple comparisons in analyzing the data in this pilot study.

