## Abstract

Title	Hyperpolarized  C pyruvate metabolic MRI for treatment response assessment in pancreatic ductal adenocarcinoma
Study Description	This is a pilot prospective study to investigate the utility of HP 13C pyruvate MRI for assessing tumor metabolism and monitoring early treatment response in patients with locally advanced or metastatic PDA.
Phase of Study	Pilot
Investigational Product	HP  C pyruvate injection
Study Population	Patients with locally advanced or metastatic pancreatic ductal adenocarcinoma (PDA) will be enrolled in parallel in one of two cohorts:
	Cohort A (N=20): Patients who are already on therapy will undergo hyperpolarized (HP) $^{13}$ C pyruvate MRI at a single time-point.
	Cohort B (N=20): Patients will undergo HP $^{13}$ C pyruvate MRI at baseline prior to the initiation of a new line of therapy (standard-of-care first- or second-line systemic therapies, radiotherapy, or therapies as part of a clinical trial), and again at 4 weeks (+/- 2 weeks) following treatment initiation.
Primary Objective	Cohort A: To determine the signal-to-noise ratio of 13C pyruvate metabolism measures (peak 13C lactate/pyruvate ratio, 13C lactate/pyruvate area-under-the- curve (AUC) ratio, and apparent rate constant for pyruvate-to-lactate conversion, kPL) in the target tumor (primary tumor and/or abdominal metastases).
	Cohort B: To determine the percent changes in the target tumor (primary tumor and/or abdominal metastases) 13C pyruvate metabolism measures (peak 13C lactate/pyruvate ratio, 13C lactate/pyruvate AUC ratio, and kPL) between pre-treatment scan and scan obtained at 4-week (+/- 2 weeks) following treatment initiation.
Secondary Objectives	Cohort A and B: To determine the repeatability of 13C pyruvate metabolism measures in the target tumor (primary tumor and/or abdominal metastasis) in patients with same-day repeated dose.
	Cohort B: To determine whether the baseline or the changes in the target tumor (primary tumor and/or abdominal metastases) 13C pyruvate metabolism measures at 4 weeks (+/-2 weeks) following treatment initiation are associated with the best objective response as defined by RECIST criteria on subsequent clinical CT scans.
Exploratory Objective	Cohort A and B: To explore 13C pyruvate metabolism between the primary tumor and abdominal metastases (when present) both at baseline and following treatment.

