## 3 Study Design

#### 3.1 Characteristics

This is a pilot prospective study to investigate the utility of HP C pyruvate MRI for assessing metabolism and monitoring early treatment response in patients with locally advanced or metastatic PDA. Patients will be enrolled in parallel in one of two cohorts:

Cohort A (N=20): Patients with locally advanced or metastatic PDA who are already on therapy will undergo hyperpolarized (HP) C pyruvate MRI at a single time-point.

Cohort B (N=20): Patients with locally advanced or metastatic PDA will undergo HP C pyruvate MRI at baseline prior to the initiation of a new line of therapy (standard-of-care first- or

second-line systemic therapies, radiotherapy, or therapies as part of a clinical trial), and again at 4 weeks (+/- 2 weeks) following treatment initiation.

In both Cohort A and B, patients may undergo an optional second dose of C pyruvate injection followed by MRI during the same imaging session.

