## 6.1 Study Calendar

Period / Procedure	Screening	Baseline HP  C pyruvate MRI		Follow up HP  C pyruvate MRI  4w ± 2w post tx initiation			Follow-Up	
		Pre- scan	HP  C MR Imaging	Post-scan	Pre- scan	HP  C MR Imaging	Post- scan	2-3mo interval tx
Study Day / Visit Day	-28d - 0d							initiation
Study Tx / Drug Admin								
HP  C pyruvate injection			Х			X 		
Administrative Procedures								
Informed consent	Х							
Clinical Assessments								
Baseline conditions	Х							
Concomitant medications	Х							
Medical history/Demographics	Х							
Performance status	Х							
Vital signs	Х	Х		X 	X 		X 	
AE assessment				X 			X 	
Laboratory Assessment								
Serum creatinine	Х							
Imaging Procedures								
MR Scan			Х			X 		
Disease Assessment on SOC CT								X 

Vital signs will be collected at the end of the visit (once the final scan is completed). AEs will be assessed following each scan.

<sup>1 Cohort B only: For patients in Cohort B, a follow up HP 13C pyruvate MRI will be obtained as per above procedures at 4 weeks (+/- 2 weeks) following the initiation of systemic therapy or radiotherapy as per clinical care.

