#### 8.3.2 Primary Analysis

Cohort A: Signal-to-noise ratio of C pyruvate metabolism measures (peak C lactate/pyruvate ratio, C lactate/pyruvate AUC ratio, and apparent rate constant for pyruvate-to-lactate conversion, kPL) in the target tumor (primary tumor and/or abdominal metastases).

Cohort B: Percent changes in the target tumor (primary tumor and/or abdominal metastases)  $^{13}$ C pyruvate metabolism measures (peak  $^{13}$ C lactate/pyruvate ratio,  $^{13}$ C lactate/pyruvate AUC ratio, and  $k_{PL}$ ) between pre-treatment scan and scan obtained at 4-week (+/- 2 weeks) following treatment initiation.

Primary endpoint analysis: For Cohort A, the signal-to-noise ratio of the target lesion C pyruvate metabolism measures will be determined for each patient. Descriptive statistics will be used to summarize the mean, standard deviation, and 95% confidence interval of the measurements.

For Cohort B, paired t-test or Wilcoxon signed rank test will be used to compare the target tumor HP C pyruvate metabolism pre- and 4-week (+/- 2 weeks) post treatment initiation.

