### 8.3.3 Secondary Analysis

Cohort A and B: Repeatability of C pyruvate metabolism measures in the target tumor (primary tumor and/or abdominal metastasis) in patients with same-day repeated dose.

Cohort B: The association between the baseline or changes in the target tumor pyruvate metabolism at 4 weeks post treatment initiation and tumor best objective response as defined according to RECIST criteria on subsequent standard-of-care CT.

Secondary endpoint analysis: For Cohort A and B, intraclass correlation coefficient (ICC) will be used to estimate the intra-subject agreement to assess repeatability of tumor HP C pyruvate metabolism in patients with same-day repeated dose.

ICC will be used to estimate agreement, and obtained from a one-way analysis of variance model based on 2 measurements per subject. The result will be presented with a 95% confidence interval. If 20 (out of 40) subjects had repeated dose of the hyperpolarized 13C pyruvate, we will have 90% power to show an ICC of at least 0.6.

For Cohort B, tumor best objective response will be defined using RECIST 1.1 on subsequent clinical CT scans. For the purpose of response assessment in this pilot study, we will group patients either as having disease control when the best response is complete response (CR), partial response (PR), or stable disease (SD) on subsequent clinical CT scans, or having disease progression when the best response is progressive disease (PD) on subsequent CT scans. Based on prior published studies (37, 38) in PDA patients who receive first- or second-line therapies (i.e. FOLFIRINOX, gemcitabine plus nab-paclitaxel, or gemcitabine monotherapy), we estimate an average 50% disease control rate for this group of patients. We will compare the baseline or changes in the target tumor C pyruvate metabolism at 4 week (+/-2 weeks) after treatment initiation between the disease control group and disease progression group (as defined by RECIST on subsequent clinical CT scans) using the Mann-Whitney tests.

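### When the new therapy in Cohort B is radiotherapy, the plan does not ensure that the analysed lesion was in the treated field

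*Combined protocol and SAP*

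**What the plan says.** The Abstract defines the new line of therapy for Cohort B as "standard-of-care first- or second-line systemic therapies, radiotherapy, or therapies as part of a clinical trial", and section 3.1 repeats this. The study calendar (section 6.1, footnote 1) times the second scan at 4 weeks, plus or minus 2 weeks, "following the initiation of systemic therapy or radiotherapy as per clinical care". Neither place limits the site of radiotherapy or says whether systemic therapy is given with it.

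The lesion rule is in section 8.3. It begins "In this pilot study, we will focus on the primary PDA HP" pyruvate measurement, where a primary is present, and continues: "If the primary tumor has been resected, we will then focus our analysis on the largest abdominal metastasis that is amenable to HP MRI". The reason given is that conventional imaging assesses response in the primary poorly. The treated field is not mentioned.

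The endpoint text in section 8.3.2 is looser: "Percent changes in the target tumor (primary tumor and/or abdominal metastases".

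Eligibility (section 3.4.1) asks for one abdominal target lesion of at least 1 cm and does not ask that it be irradiated. The replacement policy (section 3.3) covers patients who receive no treatment after the baseline scan, but not a lesion that local treatment leaves out. The study calendar has no item for the radiotherapy site, and section 8.3.2 does not separate patients by type of treatment.

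**The concern.** The Cohort B primary endpoint is meant to measure metabolic change in the target tumor after a new therapy starts. Systemic therapy can be taken to reach every lesion; radiotherapy acts on the lesions in its field. A lesion rule that ignores the field is therefore adequate for systemic therapy but not for radiotherapy given without it.

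Consider a metastatic patient whose new line is radiotherapy to a site other than the primary, with no systemic therapy and the primary still in place. Followed as written, section 8.3 analyses the primary. That pair enters the paired test with the same weight as any other, although its lesion did not receive the new therapy. The same measurement then goes into the association with response in section 8.3.3. With 20 evaluable patients, a few such pairs would matter.

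**Working it through.** **Inputs.** From section 8.1.1: n = 20 evaluable pairs, two-sided alpha 0.05, paired t-test, 80% power, standardized difference 0.38. Not in the documents, so assumed: k, the number of pairs whose analysed lesion was not treated; zero mean change in those lesions; the same SD of change (set to 1) in both groups.

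**Step 1: the plan's own figure.** Power is the probability that a noncentral t variable, with n − 1 degrees of freedom and noncentrality d√n, lies beyond the two-sided 5% critical values.

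- For d = 0.38 and n = 20, the noncentrality is 0.38 × √20 = 1.70 and power is 36%, not 80%.
- 80% power at n = 20 needs d = 0.66 (noncentrality 0.66 × √20 = 2.95). For d = 0.38 it needs 57 pairs.
- The value 0.38 is recovered only if it is scaled by the SD of a single scan, with an unstated pre/post correlation of about 0.83.

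This is a separate problem, and the present point does not depend on it. I use 0.66 so that the undiluted trial starts at 80%.

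**Step 2: dilution.** Let f = k/20. The pooled mean change is (1 − f)d and the pooled SD is √(1 + d²f(1 − f)). With d = 0.660, so that d² = 0.436:

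- k = 1: mean 0.95 × 0.660 = 0.627; SD √(1 + 0.436 × 0.0475) = 1.010; ratio 0.621.
- k = 2: mean 0.90 × 0.660 = 0.594; SD √(1 + 0.436 × 0.09) = 1.019; ratio 0.583.
- k = 4: mean 0.80 × 0.660 = 0.528; SD √(1 + 0.436 × 0.16) = 1.034; ratio 0.511.

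**Step 3: power with the untreated pairs kept, and with them left out (d = 0.66, n = 20 − k).**

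| k of 20 | Fall in mean change | Power, all 20 kept | Power, k left out | Gain in points |
|---|---|---|---|---|
| 0 | 0% | 80.0% | 80.0% | 0 |
| 1 | 5% | 75.0% | 77.7% (n = 19) | 2.7 |
| 2 | 10% | 69.6% | 75.2% (n = 18) | 5.6 |
| 4 | 20% | 58.2% | 69.5% (n = 16) | 11.3 |

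The mixture is not exactly normal, so the table was checked by simulation of 100,000 trials per setting. Power was 69.6% at k = 2 and 58.4% at k = 4, which agrees.

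**Step 4: the same with the plan's 0.38.** Power is 36.5% at k = 0, and 33.3%, 30.3% and 24.8% at k = 1, 2 and 4. Leaving the pairs out gives 34.8%, 33.1% and 29.6%. The pattern is the same from a lower start.

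**The case against.** The strongest reply is that the problem may never arise. It needs a patient whose new line is radiotherapy, without systemic therapy, and whose analysed lesion is outside the field. The documents give no count for any of these. Section 1.3 calls systemic chemotherapy the only life-prolonging treatment for this population, and the 50% disease control estimate in section 8.3.3 rests on systemic regimens only, so the authors may expect few such patients. If the irradiated lesion is the primary, the primary-first rule gives a valid pair. This stands, and it is why k is an assumed range.

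A reader might go further and infer that some pairs do measure an untreated tumor, or that the primary is always the lesion analysed. The documents support neither. The first is only a possibility that the plan leaves open. On the second, section 8.3 speaks of a focus, and section 8.3.2 allows the primary, metastases or both. That looser wording is not a safeguard, though, because it does not direct the analyst to the treated lesion.

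A reader might also infer that patient-level RECIST gives the wrong label when an irradiated tumor responds but disease progresses elsewhere. Section 8.3.3 defines the comparison group as patients "having disease progression when the best response is progressive disease (PD) on subsequent CT scans". Whole-patient progression is the correct RECIST label for that prespecified outcome, and lesions and patients can also disagree under systemic therapy. Using the diameter change of the irradiated lesion for these patients alone would mix two outcome definitions in about 20 patients, with no cutoff to form the two groups. It would also rely on size in a tumor whose size, by sections 1.3 and 8.3, is a poor guide to response.

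Finally, leaving pairs out does not restore 80% power. Without replacement the gain is about 3 to 11 points over the range shown.

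**Conclusion.** The gap is real but conditional. The plan admits radiotherapy as a new line and selects the lesion without regard to the treated field, so it does not ensure that the analysed lesion received the new therapy. A patient irradiated elsewhere without systemic therapy would pull the primary estimate toward no change.

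The size cannot be known from the documents. One, two or four such pairs of 20 would reduce the mean change by 5%, 10% or 20%, and power from 80% to about 75%, 70% or 58%. These figures assume a change of 0.66 SD in treated lesions, none in untreated lesions, and equal SDs. If untreated lesions move in the opposite direction to treated ones the dilution is greater; if they move in the same direction it is less. The correction is worth making because it is cheap and decides in advance which lesion counts.

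**What to change.** In section 8.3, state that for Cohort B patients whose new therapy is radiotherapy without concurrent systemic therapy, the analysed lesion is the primary if it was in the treated field, and otherwise the largest irradiated abdominal lesion amenable to HP MRI. If no measurable abdominal lesion was irradiated, list the patient, leave them out of the pre/post test, and treat them as unevaluable for the primary endpoint. Section 8.1.2 already allows further enrollment in that case. Bring the endpoint wording in section 8.3.2 into line with the rule.

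Record the treatment type and the irradiated lesion from the radiotherapy record, so that the choice of lesion does not depend on the measured metabolism. Keep patient-level RECIST best response as the outcome in section 8.3.3. Repeat the primary and association analyses in systemic-therapy patients only, as a sensitivity analysis.

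The cost is analysis wording and a small addition to data collection. Patient care does not change. The downside is that an off-field patient may be lost to the primary test unless replaced.

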## 8.3.1 Analysis Population

Demographic information (e.g. age, race, height, weight, and body mass index) will be summarized using descriptive statistics.

#### 8.3.2 Primary Analysis

Cohort A: Signal-to-noise ratio of C pyruvate metabolism measures (peak C lactate/pyruvate ratio, C lactate/pyruvate AUC ratio, and apparent rate constant for pyruvate-to-lactate conversion, kPL) in the target tumor (primary tumor and/or abdominal metastases).

Cohort B: Percent changes in the target tumor (primary tumor and/or abdominal metastases)  $^{13}$ C pyruvate metabolism measures (peak  $^{13}$ C lactate/pyruvate ratio,  $^{13}$ C lactate/pyruvate AUC ratio, and  $k_{PL}$ ) between pre-treatment scan and scan obtained at 4-week (+/- 2 weeks) following treatment initiation.

Primary endpoint analysis: For Cohort A, the signal-to-noise ratio of the target lesion C pyruvate metabolism measures will be determined for each patient. Descriptive statistics will be used to summarize the mean, standard deviation, and 95% confidence interval of the measurements.

For Cohort B, paired t-test or Wilcoxon signed rank test will be used to compare the target tumor HP C pyruvate metabolism pre- and 4-week (+/- 2 weeks) post treatment initiation.

### 8.3.3 Secondary Analysis

Cohort A and B: Repeatability of C pyruvate metabolism measures in the target tumor (primary tumor and/or abdominal metastasis) in patients with same-day repeated dose.

Cohort B: The association between the baseline or changes in the target tumor pyruvate metabolism at 4 weeks post treatment initiation and tumor best objective response as defined according to RECIST criteria on subsequent standard-of-care CT.

Secondary endpoint analysis: For Cohort A and B, intraclass correlation coefficient (ICC) will be used to estimate the intra-subject agreement to assess repeatability of tumor HP C pyruvate metabolism in patients with same-day repeated dose.

ICC will be used to estimate agreement, and obtained from a one-way analysis of variance model based on 2 measurements per subject. The result will be presented with a 95% confidence interval. If 20 (out of 40) subjects had repeated dose of the hyperpolarized 13C pyruvate, we will have 90% power to show an ICC of at least 0.6.

For Cohort B, tumor best objective response will be defined using RECIST 1.1 on subsequent clinical CT scans. For the purpose of response assessment in this pilot study, we will group patients either as having disease control when the best response is complete response (CR), partial response (PR), or stable disease (SD) on subsequent clinical CT scans, or having disease progression when the best response is progressive disease (PD) on subsequent CT scans. Based on prior published studies (37, 38) in PDA patients who receive first- or second-line therapies (i.e. FOLFIRINOX, gemcitabine plus nab-paclitaxel, or gemcitabine monotherapy), we estimate an average 50% disease control rate for this group of patients. We will compare the baseline or changes in the target tumor C pyruvate metabolism at 4 week (+/-2 weeks) after treatment initiation between the disease control group and disease progression group (as defined by RECIST on subsequent clinical CT scans) using the Mann-Whitney tests.

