## 2.3 Secondary Objectives and Endpoints

Secondary Objective	Endpoint(s)	Time Frame

 
To determine the repeatability of C pyruvate metabolism measures in the target tumor (primary tumor and/or abdominal metastasis) in patients with same-day repeated dose in Cohort A and B.
 
	
 
repeatability of C pyruvate metabolism measures in the target tumor
 
	From study initiation to enrollment of last subject
2. To determine whether the baseline or the changes in the target tumor (primary tumor and/or abdominal metastases)  C pyruvate metabolism at 4 weeks following treatment initiation are associated with the best objective response as defined by RECIST criteria on subsequent clinical CT scans in Cohort B.	
 
The association between the baseline target tumor pyruvate metabolism and tumor best objective response as defined according to RECIST criteria on subsequent standard-of-care CT.
 
The association between the changes in the target tumor pyruvate metabolism post treatment initiation and tumor best objective response as defined according to RECIST criteria on subsequent standard-of-care CT.
 
	From study initiation to up to 18 months following enrollment of last subject

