#### 6.3.2 Treatment Period

#### 6.3.2.1 Study Procedures, Baseline HP C pyruvate MRI

- Pre-Scan
  - Clinical Assessments
    - Vital signs including blood pressure and heart rate

Before vital signs are measured, the subject should be resting for at least 5 minutes (if possible). The same position will be used each time vital signs are measured for a given subject and blood pressure will be measured from the arm contra-lateral to the site of IMP administration whenever possible.

• Standard MR Scan

Patient is transferred to the MRI suite. Standard 1H MRI exam will be obtained in the abdomen, including T2 weighted imaging, and T1 weighted imaging pre and dynamically following gadolinium contrast administration (gadobutrol at 0.1ml/Kg body weight). If the patient has estimated glomerular filtration rate (eGFR) < 30, gadobutrol will not be administered.

- HP C MR Imaging
  - Study Tx / Drug Admin: Hyperpolarized 13C pyruvate injection

Hyperpolarized 13C pyruvate will be injected intravenously at a dose of 0.43 mL/kg and at a rate of 5 mL/second followed by a 20 mL saline flush at 5 mL/second. The volume to be injected is based upon body weight and is outlined in Appendix 2.

- Imaging Procedures: Dynamic 13C MR imaging
  - 1-2 minutes post-injection
  - 13C 3D MRI sequence with Multiband spectral-spatial excitation pulse for minimal [1-13C] pyruvate saturation and echo-planar imaging (EPI) readout for accelerated spectral-spatial sampling.
  - An optional second HP 13C pyruvate injection and MRI acquisition will be performed within 15 to 60 minutes following completion of the first scan. This repeat injection and scan is optional. This second injection will only occur if there is no adverse reaction to the first injection. The optional second injection and MRI scan are used to assess the repeatability of tumor HP 13C pyruvate metabolism.

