## 6.3.2.2 Study Procedures, Follow-Up HP C pyruvate MRI (cohort B only)

For patients in Cohort B, a follow up HP 13C pyruvate MRI will be obtained as per above procedures at 4 weeks (+/- 2 weeks) following the initiation of systemic therapy or radiotherapy as per clinical care.

- Pre-Scan
  - o Clinical Assessments
    - Vital signs including blood pressure and heart rate

Before vital signs are measured, the subject should be resting for at least 5 minutes (if possible). The same position will be used each time vital signs are measured for a given subject and blood pressure will be measured from the arm contra-lateral to the site of IMP administration whenever possible.

Standard MR Scan

Patient is transferred to the MRI suite. Standard 1H MRI exam will be obtained in the abdomen, including T2 weighted imaging, and T1 weighted imaging pre and dynamically following gadolinium contrast administration (gadobutrol at 0.1ml/Kg body weight). If the patient has estimated glomerular filtration rate (eGFR) < 30, gadobutrol will not be administered.

- HP C MR Imaging
  - o Study Tx / Drug Admin: Hyperpolarized 13C pyruvate injection

Hyperpolarized 13C pyruvate will be injected intravenously at a dose of 0.43 mL/kg and at a rate of 5 mL/second followed by a 20 mL saline flush at 5 mL/second. The volume to be injected is based upon body weight and is outlined in Appendix 2.

- Imaging Procedures: Dynamic 13C MR imaging
  - 1-2 minutes post-injection
  - 13C 3D MRI sequence with Multiband spectral-spatial excitation pulse for minimal [1-13C] pyruvate saturation and echo-planar imaging (EPI) readout for accelerated spectral-spatial sampling.
  - An optional second HP 13C pyruvate injection and MRI acquisition will be performed within 15 to 60 minutes following completion of the first scan. This repeat injection and scan is optional. This second injection will only occur if there is no adverse reaction to the first injection. The optional second injection and MRI scan are used to assess the repeatability of tumor HP 13C pyruvate metabolism.

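### Same-day repeatability is reported only as an ICC; a within-subject CV and repeatability coefficient from the same pairs would show scan-to-scan error in the percent units of the Cohort B endpoint

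*Combined protocol and SAP*

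**What the plan says.** Repeatability is the first secondary objective in section 2.3, to be assessed "in patients with same-day repeated dose in Cohort A and B". The data come from an optional second injection and scan, which "will be performed within 15 to 60 minutes following completion of the first scan" (section 6.3.2.1). The Cohort B follow-up visit repeats this option and its purpose: "The optional second injection and MRI scan are used to assess the repeatability of tumor HP 13C pyruvate metabolism" (section 6.3.2.2).

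Section 8.3.3 names the ICC as the only statistic: "intraclass correlation coefficient (ICC) will be used to estimate the intra-subject agreement to assess repeatability of tumor HP" 13C pyruvate metabolism. It is to be "obtained from a one-way analysis of variance model based on 2 measurements per subject" and reported with a 95% confidence interval. The section adds that if 20 of the 40 subjects have a repeat dose, "we will have 90% power to show an ICC of at least 0.6". No within-subject SD or CV, repeatability coefficient or limits of agreement appears anywhere in the documents.

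In section 8.3.2 the Cohort B primary endpoint is "Percent changes in the target tumor (primary tumor and/or abdominal metastases") for three measures: peak lactate/pyruvate ratio, lactate/pyruvate AUC ratio and kPL.

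**The concern.** An ICC is the share of total variance that lies between patients. It rises when the enrolled patients are more varied, even if the scanner is no more precise. The same-day analysis combines patients already on therapy (Cohort A) with patients starting a new line (Cohort B). Section 8.3 uses the primary tumor where present and otherwise the largest suitable abdominal metastasis. Between-patient spread will therefore depend partly on who accepts the optional second scan.

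The same-day pairs are the plan's only test-retest data. The other technical measure, "For Cohort A, the signal-to-noise ratio of the target lesion" metabolism, describes signal quality and not the difference between two scans of one patient. Someone reading a Cohort B change of a given percentage, or planning a later study, would want to know how far two scans in one session differ in percent. An ICC alone does not tell them.

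A smaller ambiguity is that a Cohort B patient may have a same-day pair at both visits, and section 8.3.3 does not say which pair supplies the two measurements.

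**Working it through.** **The plan's own figure.** Inputs from section 8.3.3: n = 20 subjects, k = 2 measurements, ICC = 0.6, power 90%. The null value, alpha and sidedness are not stated. For the exact one-way F test with 19 and 20 degrees of freedom against ICC = 0 at one-sided 0.05, the critical value is 2.137. At a true ICC of 0.6 the ratio (1 + 0.6)/(1 - 0.6) is 4, so power = P(F > 2.137/4) = P(F > 0.534) = 91.1%. This is close to the stated 90%. The two-sided 0.05 version gives 84.8%. Read this way, 0.6 is the true value assumed for planning, tested against zero, and not a limit of acceptable scan error.

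**From ICC to percent error.** Let b be the between-patient SD and w the within-patient SD, both on the log scale. The documents give neither, so b = 0.2, 0.4 and 0.6 are assumptions.

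- ICC = b²/(b² + w²), so w = b × √((1 - ICC)/ICC). At ICC = 0.6, w = b × √(0.4/0.6) = 0.8165b.
- Within-subject CV = √(exp(w²) - 1).
- Same-session 95% limits = exp(±1.96 × √2 × w) - 1.

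| Assumed b | w at ICC 0.6 | Within-subject CV | 1.96√2 × w | Limits |
|---|---|---|---|---|
| 0.2 | 0.163 | 16% | 0.453 | -36% / +57% |
| 0.4 | 0.327 | 34% | 0.905 | -60% / +147% |
| 0.6 | 0.490 | 52% | 1.358 | -74% / +289% |

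**The reverse direction.** Fix the precision at w = 0.20. The limits are exp(±0.554) - 1 = -43%/+74% in every case, yet the ICC is 0.04/0.08 = 0.50, 0.16/0.20 = 0.80 or 0.36/0.40 = 0.90 for the same three values of b.

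**Scale check.** Section 8.3.3 does not mention a log transform. Under the same lognormal assumptions the raw-scale ICC is (exp(b²) - 1)/(exp(b² + w²) - 1). The three rows then give 0.59, 0.57 and 0.53 instead of 0.6. The limits illustrate a log-scale ICC of 0.6 and are not exactly what a raw-scale ICC of 0.6 would imply.

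**Precision of the added statistic.** With n pairs and n degrees of freedom, the 95% interval for w, and so for the log-scale coefficient, is √(n/χ²) times the estimate at the 0.975 and 0.025 points.

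- n = 20: √(20/34.17) = 0.77 to √(20/9.59) = 1.44.
- n = 10: √(10/20.48) = 0.70 to √(10/3.247) = 1.75.
- Removing the mean first-to-second difference costs one degree of freedom; with 20 pairs the range becomes 0.76 to 1.46.

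For comparison, an observed ICC of 0.6 from 20 pairs has a 95% interval of about 0.23 to 0.82, so the ICC is imprecise too.

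**The case against.** The strongest reply is that nothing here is wrong. The objective says only repeatability, and an ICC with a confidence interval answers it. The Cohort B primary test works at group level, and the observed spread of the changes already contains scan-to-scan and visit-to-visit noise, so its inference needs no repeatability coefficient. The same holds for the Mann-Whitney comparisons, and the ICC is itself relevant when baseline values are compared between patients. All of this stands, and it makes the point an improvement to reporting and not a correction.

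Two further objections also stand in part. The limits above rest on assumed SDs and a log scale; the dependence of the ICC on between-patient spread does not. Section 8.3 already provides for listings of all dosed subjects, so if paired values are listed a coefficient could be computed later. That would leave it unspecified in advance.

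A reader might go further and infer that individual patients will be wrongly called changed or unchanged. The documents do not support this: no section applies an individual threshold, and the reporting paragraph in section 6.3.2.2 keeps the research scan out of clinical management. A reader might also assume that the planned ANOVA already supplies the coefficient. It is not stated to be on the log scale, so its within-subject mean square does not directly give percent limits.

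**Conclusion.** The point holds as a worthwhile, low-cost addition to section 8.3.3. The ICC alone leaves the size of scan-to-scan error in percent undetermined: under the assumed spreads, one ICC value fits limits from -36%/+57% to -74%/+289%, and one precision fits ICCs from 0.50 to 0.90. That the ICC does not fix the percent error is algebra; the particular figures depend on the assumed log-SDs. No sample size, power statement or planned test changes.

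**What to change.** In section 8.3.3:

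- Keep the ICC, its 95% confidence interval and its power statement.
- For each of the three measures, add the within-subject CV and the 95% repeatability coefficient with a confidence interval. Compute them from log differences within each same-session pair and back-transform to percent limits; use the raw scale if the error proves additive.
- Report the mean first-to-second difference with its confidence interval, because a one-way model counts a systematic shift as within-subject error.
- Use one pre-specified pair per patient for the ICC where a Cohort B patient has pairs at both visits.
- State that same-session scans omit visit-to-visit variation. The limits are then descriptive and probably, though not certainly, understate the noise in a 4-week change.

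The cost is a few lines of SAP text and one small extra analysis, with no added patients, injections or scans. The downside is the imprecision shown above. The second scan is optional, so 20 pairs are not assured, and the coefficient should never be shown without its interval.
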